8.2.1 Individual Discontinuation Criteria

- A participant may withdraw completely from the study at any time at his/her own request, or may be withdrawn at any time at the discretion of the investigator for safety, behavioral, compliance, or administrative reasons. This is expected to be uncommon. Stopping study intervention is not considered withdrawal from the study.
- At the time of discontinuing from the study, if possible, an early termination visit should be conducted, as shown in the Schedule of Activities. See the Schedule of Activities for data to be collected at the time of study discontinuation and follow-up and for any further evaluations that need to be completed.
- The participant will be permanently discontinued both from the study intervention and from the study at that time.
- If the participant withdraws consent for disclosure of future information, the Sponsor may retain and continue to use any data collected before such a withdrawal of consent.

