8 DISCONTINUATION CRITERIA

8.1 Discontinuation from Study Intervention

Participants MUST discontinue IP (and Non-IP/AxMP at the discretion of the investigator) for any of the following reasons:

- Participant's request to stop study intervention. Participants who request to discontinue study
 intervention will remain in the study and must continue to be followed for protocol-specified
 follow-up procedures. The only exception to this is when a participant specifically withdraws
 consent for any further contact with him/her or persons previously authorized by the participant
 to provide this information
- Any clinical AE, laboratory abnormality, or intercurrent illness which, in the opinion of the investigator, indicates that continued participation in the study is not in the best interest of the participant
- Termination of the study by BMS
- Loss of ability to freely provide consent through imprisonment or involuntarily incarceration for treatment of either a psychiatric or physical (eg, infectious disease) illness. (Note: Under specific circumstances and only in countries where local regulations permit, a participant who has been imprisoned may be permitted to continue as a participant. Strict conditions apply, and BMS approval is required)
- Participant reports suicidal ideation, suicidal behavior, or suicide attempts at any time after randomization. The participant should then be immediately referred to a mental health professional for evaluation of suicide risk
- Abnormal liver tests suggestive of drug-induced liver injury (DILI), or if the investigator believes that it is in the best interest of the participant
- Malignancy; however, a participant who develops non-melanoma skin cancer may continue in the study at the discretion of the investigator
- Pregnancy, positive pregnancy test, or participant expresses an interest in becoming pregnant
- Participant develops active TB during the study or prematurely discontinues treatment for LTBI, or participant is noncompliant with LTBI therapy
- Japan only: Participant with positive HBsAb at Screening or positive HBcAb with negative or undetectable HBV DNA (< 1.3 Log IU/mL [20 IU/mL]) at Screening, for whom quantitative

45

Protocol Amendment No.: 02 Date: 29-Aug-2023

HBV DNA becomes detectable ($\geq 1.3~Log~IU/mL$ ([20 IU/mL]) at any time during treatment with the IP

- Inability or failure to comply with protocol requirements, in the opinion of the investigator

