10 STATISTICAL CONSIDERATIONS

10.1 Statistical Hypothesis

Let μ_1 and μ_2 be the population means of change from baseline at Week 24 in SALT for 6 mg QD and 6 mg BID dosages of deucravacitinib, respectively, and μ_0 be the population mean of change from baseline at Week 24 in SALT for placebo; the 2 primary hypotheses for this study are:

- 1) $H0_1$: $\mu_1 = \mu_0$ versus $H1_1$: $\mu_1 \neq \mu_0$
- 2) $H0_2$: $\mu_2 = \mu_0$ versus $H1_2$: $\mu_2 \neq \mu_0$

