10.2 Sample Size Determination

Approximately 90 participants will be randomized on Day 1 in a 1:1:1 ratio, resulting in 30 participants in each deucravacitinib dose arm (6 mg QD and 6 mg BID) and 30 participants in the placebo arm.

Assuming a 39-point difference in change in SALT score from baseline to Week 24 between both deucravacitinib doses and placebo, and a common standard deviation (SD) of 43 points, the following table presents 2 scenarios on sample size and overall power of the study.

Type I error	Sample Size	Overall Power
0.10	25	93%
0.05	25	88%

Protocol Amendment No.: 02

Date: 29-Aug-2023

Assuming a 15% drop out rate and an overall type I error of 0.10 level:

1) Without multiplicity adjustment for 2 doses to be compared with the placebo, the study overall power with a sample size of 30 in each arm is 93%

2) With Bonferroni adjustment for 2 doses to be compared with the placebo, the study overall power with a sample size of 30 in each arm is 88%

The expected difference (39 points) between deucravacitinib dose and placebo and common SD (43 points) in the change from baseline in the SALT score are based on an average of recently reported data from clinical trials with oral compounds in participants with moderate to severe AA treated with an oral TYK2/JAK1 inhibitor, PF-06700841 (placebo-adjusted mean 49.5 points, 95% confidence interval [CI] [37.1, 61.8]), and with an oral JAK 3 inhibitor, PF-06651600 (placebo-adjusted mean 33.6 points, 95% CI [21.4, 45.7]) compared to placebo.¹⁸

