10.4.2 Primary Efficacy Endpoints

The 2 primary hypotheses, as specified in Section 10.1, will be tested on the overall significance level of 10%. To strongly control the overall type I error at 10% level, the Bonferroni adjustment will be used to adjust multiplicity due to 2 deucravacitinib dose arms to be compared with the placebo arm.

The primary efficacy endpoint (change in SALT score from baseline to Week 24 [Day 169]) will be analyzed on the randomized population using an analysis of covariance (ANCOVA). The ANCOVA model will include treatment arm, the randomization stratification variable of alopecia episode duration (< 4 years and ≥ 4 years), as factors, and baseline SALT score as a covariate.

The primary methodology to impute the missing data will be multiple imputation with the assumption of missing at random.

Additional sensitivity analyses will be further outlined in the SAP.

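### Section 8.2.1 lets the investigator end study participation on safety and compliance grounds that Section 8.1 treats as reasons to stop drug with follow-up continuing, so an obtainable Week 24 SALT can be lost

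*Combined protocol and SAP*

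**What the plan says.** Section 8.2.1 provides that a participant "may be withdrawn at any time at the discretion of the investigator for safety, behavioral, compliance, or administrative reasons". The consequence follows in the same section: "The participant will be permanently discontinued both from the study intervention and from the study at that time". The section adds that this should be uncommon, that stopping drug does not count as leaving the study, and that an early termination visit is held where possible.

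Section 8.1 lists reasons for stopping study intervention. One is a clinical adverse event, laboratory abnormality or intercurrent illness, in the investigator's opinion. Another is "Inability or failure to comply with protocol requirements, in the opinion of the investigator". The section then says everyone who stops study intervention should follow the procedures in Table 2-3. The only exceptions are withdrawal of consent for all study procedures and loss of the ability to consent freely.

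Section 8.1.2 is weaker. It says those who stop may be followed, and names only the Week 52/early discontinuation visit and the post-treatment visit.

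Section 10.4.2 analyses Week 24 change in SALT in all randomized participants. On missing values it states: "The primary methodology to impute the missing data will be multiple imputation with the assumption of missing at random". Further sensitivity analyses are left to the SAP.

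**The concern.** Safety and non-compliance appear in both sections with different consequences for data collection. The protocol gives no rule for choosing between them, so sites may handle similar participants differently, and a participant who has not withdrawn consent can be removed from outcome collection.

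If that happens before Week 24, the primary endpoint is missing although it could have been observed. Exits for tolerability or compliance may depend on treatment arm and on how the participant was doing. Missing-at-random imputation is reliable only if the data in the imputation model account for that dependence. A sensitivity analysis can probe the assumption but cannot recover the value. With 30 per arm, each participant carries visible weight.

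**Working it through.** **1. The two routes compared**

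| | Section 8.1 | Section 8.2.1 |
|---|---|---|
| Safety | AE, laboratory abnormality or illness | listed |
| Compliance | failure to comply | listed |
| Behavioral, administrative | no close counterpart | listed |
| Effect | study intervention stops | study intervention and study both end |
| Follow-up | should continue, two exceptions | early termination visit if possible |

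The overlap covers two of the four grounds. Investigator discretion is not among the exceptions in Section 8.1, yet Section 8.2.1 uses it to end follow-up. The AE ground in Section 8.1 blurs the line further, because it asks whether continued participation in the study is in the participant's interest although the section concerns stopping drug.

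**2. What SALT data remain**

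Table 2-2 schedules SALT at Week 0 and every 4 weeks to Week 24. Footnote a of Table 2-3 calls for the Week 52 assessments, which include SALT, at early discontinuation from the study. An investigator withdrawal at, say, Week 12 therefore leaves scores up to Week 12, perhaps an exit score, and no Week 24 score. An exit after Week 24 does not affect this endpoint.

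**3. The planned power, reproduced**

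Inputs from Sections 10.1, 10.2 and 10.4.2: difference 39, SD 43, two-sided tests, overall alpha 0.10 split by Bonferroni to 0.05 per dose, 30 per arm, 15% dropout.

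- Evaluable per arm: 30 × 0.85 = 25.5, taken as 25.
- Standard error of a difference: 43 × √(2/25) = 12.2.
- Noncentral t power, n = 25 per arm: 88.1% at alpha 0.05 (plan: 88%) and 93.5% at alpha 0.10 (plan: 93%).

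The plan's figures reproduce.

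**4. Power if losses exceed the allowance**

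The plan already absorbs 0.15 × 30 = 4.5 losses per arm. Counting each further loss in every arm as contributing nothing, power at alpha 0.05 is:

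| Evaluable per arm | 25 | 24 | 23 | 22 | 21 | 20 |
|---|---|---|---|---|---|---|
| Power | 88.1% | 86.8% | 85.3% | 83.6% | 81.8% | 79.8% |

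Each further loss per arm costs about 1.4 to 2 points.

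**5. Worst-case bias (assumed)**

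Suppose k participants in one active arm are withdrawn before Week 24, would have had a placebo-like change, and are imputed at the full planned benefit. The arm's mean benefit is overstated by k/30 × 39.

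- k = 1: 1.3 points (1.3/39 = 3% of the planned effect)
- k = 2: 2.6 points (7%)
- k = 3: 3.9 points (10%)

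Against the planned standard error this is 1.3/12.2 = 0.1 to 3.9/12.2 = 0.3. The documents give no rate of investigator withdrawal, so the values of k are assumptions.

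**The case against.** The protocol does separate stopping drug from leaving the study, says investigator withdrawal should be uncommon, and lists exceptions to follow-up that do not include it. On that reading, a site that removes a consenting participant for an AE is arguably departing from Section 8.1. This has force, but an expectation is not a limit, and Section 8.2.1 grants the discretion expressly. The conflict stands.

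A reader might infer that a site using Section 8.1 keeps the primary endpoint while a site using Section 8.2.1 loses it. The documents do not support so clean a contrast. Section 8.1.2 makes follow-up optional in its wording, and Table 2-3 starts at Week 28, so a Week 24 SALT is not clearly required after a drug-only stop either. Tightening Section 8.2.1 alone would not secure the endpoint.

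A reader might also infer that no SALT is collected after an investigator withdrawal. The exit visit provides for one where possible, although it does not stand in for Week 24.

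The bias illustration is a worst case. It gives full benefit to participants whose interim and exit scores may already show non-response, and an imputation model using those scores would tend to reduce the error. The text reviewed does not specify that model or the sensitivity analyses, so neither protection can be assumed or ruled out.

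**Conclusion.** The concern holds as a conflict between Sections 8.2.1 and 8.1 on safety and compliance grounds, with avoidable loss of Week 24 SALT as the consequence. It applies only to exits before Week 24. The size is unknown. The 1.3 to 3.9 points rests on three assumptions: 1 to 3 such exits in one active arm, placebo-like outcomes in those participants, and imputation at the full planned benefit. It should not be read as an estimate of bias in the primary result.

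Nor does the point show an error in the sample size. The power figures reproduce, and investigator withdrawals may fall within the 15% already allowed. This is a cheap improvement to data retention. It does not show that the primary analysis is invalid.

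**What to change.** Reconcile Section 8.2.1 with Sections 8.1 and 8.1.2. State in all three that a participant who has not withdrawn consent and can still consent remains in outcome collection, with SALT at the scheduled Table 2-2 visits through Week 24, whatever the reason study intervention stopped. Replace the optional wording in Section 8.1.2, and refer to Table 2-2 as well as Table 2-3 for those who stop before Week 24. Leave the grounds for stopping study intervention unchanged. Record any investigator-initiated study exit, with its reason, on the CRF.

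The cost is amendment wording, a CRF reason field, and a few extra visits for participants who are off drug.

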8.3 Lost to Follow-up

The following actions must be taken if a participant fails to return to the clinic for a required study visit:

- All reasonable efforts must be made to locate participants to determine and report their ongoing status. This includes follow-up with persons authorized by the participant.
- Lost to follow-up is defined by the inability to reach the participant after a minimum of **three (3)** documented phone calls, faxes, or emails, as well as lack of response by participant to one (1) registered mail letter. All attempts should be documented in the participant's medical records.

• If it is determined that the participant has died, the site will use permissible local methods to obtain date and cause of death.

- If the investigator's use of a third-party representative to assist in the follow-up portion of the study has been included in the participant's informed consent, then the investigator may use a Sponsor-retained third-party representative to assist site staff with obtaining the participant's contact information or other public vital status data necessary to complete the follow-up portion of the study.
- The site staff and representative will consult publicly available sources, such as public health registries and databases, in order to obtain updated contact information.
- If, after all attempts, the participant remains lost to follow-up, then the last known alive date as determined by the investigator should be reported and documented in the participant's medical records.

9 STUDY ASSESSMENTS AND PROCEDURES

All Screening evaluations must be completed and reviewed to confirm that potential participants meet all eligibility criteria before randomization. The investigator will maintain a Screening Log to record details of all participants screened and to confirm eligibility or record reasons for Screening failure, as applicable.

Procedures conducted as part of the participant's routine clinical management (eg, blood count) performed before signing the informed consent may be utilized for screening purposes, provided the procedure meets the protocol-defined criteria and has been performed within the timeframe defined in Section 6.

Below is the suggested order in which to perform the evaluations at each applicable visit:

- Concomitant medications
- Adverse event monitoring
- 12-lead ECG
- Vital signs
- Body weight and height
- Physical examination and efficacy assessments. Assessments should be completed in the following order:
 - Hamilton-Norwood/Ludwig Classification
 - SALT Assessment

- AA-IGA
- Medical photography of scalp and eyebrows/eyelashes (if consent obtained)

Protocol Amendment No.: 02 Date: 29-Aug-2023

- (if consent obtained)
- Urine pregnancy test (WOCBP) and urinalysis
- Blood sampling for laboratory assessments. Please refer to regarding requirement for pre-and post-dose sample collection times
- Study intervention accountability and study intervention compliance
- Dispensing of study intervention

9.1 Efficacy Assessments

The efficacy assessments listed below are commonly used tools to characterize disease severity in patients with AA and are established endpoints in clinical practice for assessing treatment efficacy in AA

All investigator-administered assessments should be performed by a dermatologist or appropriately trained licensed health care provider who is experienced in the assessment of patients with AA. All efficacy evaluators must receive and document protocol-specific efficacy assessment training prior to performing the evaluations.

To ensure consistency and reduce variability, the same evaluator must assess all dermatological clinical evaluations for any individual participant throughout the study whenever possible; a back-up experienced, qualified, and protocol-trained evaluator will only be allowed on rare occurrences, when the designated evaluator is unable to perform the evaluation.

[figure not shown]
• SALT Assessment (Appendix 5^{32,33}) This is a quantitative rating scale for measuring the severity of terminal hair loss in each of the 4 quadrants of the scalp: posterior (back), vertex (top), left, and right profile. To obtain a SALT score, the degree of scalp hair loss is assessed as a percentage of each scalp region affected and is multiplied by its respective weighting factor (the scalp surface area) for each of the 4 sections in order to provide a subtotal for each region. The SALT score is the sum of these subtotals. SALT scores can range from 0 (no hair loss) to 100 (total scalp hair loss).

SALT50 indicates at least a 50% improvement from baseline in the SALT score at a particular time point, indicating 50% hair regrowth.

The proportion of participants achieving these responses will be assessed at all visits.

• AA-IGA: The AA-IGA utilizes a 5-point scale, in which the investigator assesses scalp hair loss based on the SALT assessment. The AA-IGA measures AA severity at a single point in time (without taking into account the baseline disease condition). The participant's scalp hair loss, as it looks at the time of evaluation, is scored as none (0) (0% scalp hair loss), limited (1) (1%-20% scalp hair loss), moderate (2) (21%-49% scalp hair loss), severe (3) (50%-94% scalp hair loss), or very severe (4) (95%-100% scalp hair loss).

Protocol Amendment No.: 02 Date: 29-Aug-2023

Protocol Amendment No.: 02 Date: 29-Aug-2023

te: 29-Aug-2023

9.1.2 Medical Photography

Medical photography of the scalp is required at the visits indicated in the Schedule of Activities. A separate consent will be required to allow for photography of a participant's face for eyelash and eyebrow evaluation at Day 1, Week 24, Week 40, and Week 52. In participants who provide optional consent, if new onset involvement of eyelashes and/or eyebrows (not present at baseline) is observed after Day 1, a photograph of the eyelashes and or eyebrows should be taken at the visit first observed, in addition to Weeks 24, 40, and 52.

An external reviewer will assess for regrowth of eyebrows and eyelashes.

Sites will be equipped with clinical photography supplies. Any photographs may be used as supplemental documentation for publications and to increase understanding of effect of study intervention on hair regrowth.

Detailed instructions on the collection and transmission of digital images will be provided to the investigator in a separate manual at or before the time of study initiation.

9.2 Adverse Events

The definitions of an AE or SAE can be found in Appendix 3.

AEs will be reported by the participant (or, when appropriate, by a caregiver, a surrogate, or the participant's legally acceptable representative).

The investigator and any qualified designees are responsible for detecting, documenting, and reporting events that meet the definition of an AE or SAE and remain responsible for following up AEs that are serious, considered related to the study intervention or the study, or that caused the participant to discontinue before completing the study.

Refer to Appendix 3 for SAE reporting.

9.2.1 Adverse Events of Interest

Adverse events of interest (AEIs) are AEs for a particular product or class of products that a Sponsor may wish to monitor more carefully. AEIs may be serious or nonserious and may require further investigation to better characterize and understand them. In the deucravacitinib clinical development program, select infections (opportunistic, TB, herpes zoster) and malignancies have been identified as AEIs based on the mechanism of action of deucravacitinib. Therefore, in order to better characterize and understand these AEIs, information may be collected on supplemental CRFs. Additionally, information on potential AEIs based on the disease or population under study may be collected on supplemental CRFs.

9.2.2 Time Period and Frequency for Collecting AE and SAE Information

All SAEs must be collected from the time of signing the consent, including those thought to be associated with protocol-specified procedures, and within 30 days following discontinuation of dosing.

The investigator must report any SAE that occurs after these time periods and that is believed to be related to study intervention or protocol-specified procedure (eg, a follow-up skin biopsy,).

• Medical occurrences that begin before the start of study intervention but after obtaining informed consent will be recorded on the appropriate section of the CRF module.

- All SAEs will be recorded and reported to Sponsor or designee within 24 hours, as indicated in Appendix 3.
- The investigator will submit any updated SAE data to the sponsor or designee within 24 hours of updated information being available.

Investigators are not obligated to actively seek AEs or SAEs in former study participants. However, if the investigator learns of any SAE, including a death, at any time after a participant has been discontinued from the study, and he/she considers the event reasonably related to the study intervention or study participation, the investigator must promptly notify the Sponsor.

The method of evaluating and assessing causality of AEs and SAEs and the procedures for completing and reporting/transmitting SAE reports are provided in Appendix 3.

In order to facilitate enhanced reporting of COVID-19 events that occur during the study, all AEs and SAEs reported after the time of consent that are related to SARS-CoV-2 or COVID-19 infection must be reported (Section 9.2).

9.2.3 Method of Detecting AEs and SAEs

AEs can be spontaneously reported or elicited during open-ended questioning, examination, or evaluation of a participant. Care should be taken not to introduce bias when collecting AE and/or SAEs. Inquiry about specific AEs, should be guided by clinical judgment in the context of known AEs, when appropriate for the program or protocol.

